2.5 Pain assessment and the numeric pain rating scale (NPRS)

In the conventional radiation setting, the International Consensus Pain Response Endpoints (ICPRE) has been developed for clinical endpoints as pain for bone metastases²¹. In this protocol, we will use the ICPRE to evaluate pain response. Response categories are based on patient reported pain scores (NPRS) and analgesic consumption (convert to oral morphine-equivalent dose).

NPRS ranges from '0' representing one pain extreme (e.g. "no pain") to '10' representing the other pain extreme (e.g. "pain as bad as you can imagine" or "worst pain imaginable"). See Appendix C.

Registration of NPRS will be registered at baseline and subsequently according to Table 2. Analysis of pain reduction will only include patients with $\text{NPRS} \geq 1$ registered at baseline. We intend to report the best response during follow-up. If more than one lesion is treated, the index lesion will be used to assess the pain response. The index lesion is defined as the lesion with the highest pretreatment pain score. If a patient has two or more lesions with the same maximum pain score, the index lesion is defined as the most cranial located lesion.

- A complete pain response is defined as a pain score of 0 out of 10 at the treated site with no concomitant increase in analgesic intake
- A partial pain response is defined as a pain reduction of 2 or more at the treated site without analgesic increase, or an analgesic reduction of 25% with no increase in pain score or 1 point above baseline.
- Pain progression is defined as an increase in pain score of 2 or more above baseline with stable analgesic intake or an analgesic increase of 25% with stable pain score.
- An indeterminate response is any response not captured in the above definitions.

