2. To investigate if there is a difference in pain response, weight, primary treatment site re-irradiation, quality of life and overall survival in patients treated with esophagus-sparring radiotherapy compared to patients receiving standard treatment.

3. To describe the dose-response relationship for the esophagus in the palliative dose spectrum.
4. To investigate if esophagus-sparring radiotherapy will increase other toxicities compared to standard radiotherapy.

Primary endpoints

Co-primary endpoints are

- a. Peak patient reported dysphagia (PRO-CTC-AE version 1) within the first five week after treatment start.
- b. Ability to walk, measured by the mobility dimension of the EQ-5D-5L questionnaire.

Secondary endpoints

- Quality of life, measured by EORTC-QLQ-C30 and EQ-5D-5L
- Nausea and dyspepsia measured by PRO-CTC-AE Version 1.0
- Treatment site pain response measured by International Consensus Pain Response Endpoints (ICPRE)
- Patient reported toxicity reported in PRO-CTC-AE-Version 1.0 “Other symptoms” section
- CTC-AE* Version 5: Cough, dyspnea, dyspepsia, dysphagia, hoarseness, oropharyngeal pain
- Changes in weight
- Consumption of corticosteroids, antacids and antiemetics
- Treatment site re-irradiation rate
- Hospitalization rate
- Overall survival

*Registered from patient no. 107

Trial design

The trial is designed as a phase III, randomized, single-blind clinical trial, clinicaltrials.gov ID No. NCT051098.

The trial is performed in a public health care system including two academic cancer centers treating MSCC. The individual centers are started at different times due to logistics. Patients are randomized 1:1 to either esophagus-sparring treatment or standard treatment. Patients are followed actively for 9 weeks after treatment start. Dysphagia, nausea and dyspepsia from the NCI PRO-CTC-AE Version 1.0 library and treatment site pain (Numeric Pain Rating Scale) are reported daily for 5 weeks and subsequently weekly for 4 weeks. Quality of life (EQ-5D-5L and QLQ-C30), use of medication (glucocorticoid, antiemetic, analgesic) and weight are reported weekly for 9 weeks, **Table 1**.

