For each of the first five weeks, where daily measurements are recorded, the peak value will be used for analysis. Changes in severity score over time (repeated measurement) will be analyzed using Generalized Linear Mixed Models.

C. Duration of dysphagia, nausea and dyspepsia measured by NCI-PRO-CTC-AE [Time Frame: within five weeks after start of RT (daily measurements) and at 6, 7, 8, and 9 weeks].

Duration of toxicity will be presented graphically in separate figures.

For the first five weeks mean duration (days) in each group will be compared using Wilcoxon rank-sum test.

D. Severity of cough, oropharyngeal pain, dyspnea, dysphagia, hoarseness, and dyspepsia measured by CTC-AE (weekly measurements) [Time Frame: Week 1-5 after start of radiotherapy (repeated measurement)].

CTC-AE responses are scored from 0 to 4, with 0 representing “None” and 4 representing “Very severe”.

Changes in severity score over time (repeated measurement) will be analyzed using Generalized Linear Mixed Models.

E. Duration of cough, oropharyngeal pain, dyspnea, dysphagia, hoarseness, and dyspepsia measured by CTC-AE (weekly measurements) [Time Frame: Week 1-5 after start of radiotherapy (repeated measurement)].

Duration of toxicity will be presented graphically in separate figures. Mean duration (weeks) in each group will be compared using Wilcoxon rank-sum test.

F. Demographics: Subject demographics, baseline characteristics and medical history will be summarized descriptively. Generally, range, mean and standard deviation, or median and inter quartile range, will be reported for continuous variables. Frequencies and proportions will be reported for categorical variables.

G. Treatment site pain response [Time frame: weekly, 1-9 weeks after start of RT]:

Only patients with baseline pain will be included in the analysis.

Pain response will be measured by the ICPRE score (6). Possible responses are “Complete response”, “Partial response”, “Pain Progression” and “Intermediate response”.

For each of the first five weeks, where daily measurements are recorded, the worst response will be used for analysis. Changes in ICPRE score over time (repeated measurement) will be analyzed using Generalized Linear Mixed Models.

H. Duration of treatment site pain response [Time Frame: Weekly week 1-9 after start of radiotherapy].

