Primary Ambulatory function	EQ-5D-5L mobility dimension	At nine weeks after start of radiotherapy	Ordinal	Wilcoxon rank-sum test
Severity of dysphagia, nausea, and dyspepsia	NCI-PRO-CTC-AE	Weekly, week 1-9 after start of radiotherapy	Ordinal, repeated measurement	Generalized Linear Mixed Models
Duration of dysphagia, nausea, and dyspepsia	NCI-PRO-CTC-AE	Within five weeks after start of RT (daily measurements) and at 6, 7, 8, and 9 weeks	Continuous, mean [range]	Descriptive graphical presentation and Wilcoxon rank-sum test for group comparison
Severity of cough, dyspnea, dyspepsia, dysphagia, hoarseness, oropharyngeal pain	NCI-CTC-AE	Weekly, week 1-5 after start of radiotherapy	Ordinal, repeated measurement	Generalized Linear Mixed Models
Duration of cough, dyspnea, dyspepsia, dysphagia, hoarseness, oropharyngeal pain	NCI-CTC-AE	Weekly, week 1-5 after start of radiotherapy	Continuous, mean [range]	Descriptive graphical presentation and Wilcoxon rank-sum test for group comparison
Pain response, severity	ICPRE score	Weekly, week 1-9 after start of radiotherapy	Ordinal, repeated measurement	Generalized Linear Mixed Models

Quality of life	EQ-5D-5L	Weekly, week 1-9 after start of radiotherapy	Categorical (index), and Visual analog scale (continuous)	As per described in EQ-5D-5L guidelines (7) Combined index is calculated using Denmark as reference. Changes in EQ-index value and VAS-score over time (repeated measurement) will be analyzed with Generalized Linear Mixed Models.
Quality of Life	EORTC-QLQ-C30	Weekly, week 1-9 after start of radiotherapy	Categorical (raw QLQ-C30 scores) and Continuous (the raw QLQ-C30 scores can be transformed to scores ranging from 0 to 100)	As per described in EORTC-QLQ-C30 guidelines (8). Descriptive statistics of QLQ-C30 domains and analysis of changes over time with Generalized Linear Mixed Models
Weight	Change in kg from baseline	Weekly, week 1-9 after start of radiotherapy	Continuous, repeated measurement	Linear Mixed Effects Models
Hospitalization rate	Days hospitalized of days alive (absolute numbers and %)	Week 1-9	Continuous, mean [range]	Wilcoxon rank-sum test
Re-irradiation rate, primary site	Number of patients receiving re-irradiation in each arm (absolute numbers and %)	3, 6- and 12-months after inclusion	Continuous, mean [range]	Wilcoxon rank-sum test

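### Pain response: the protocol reports the best response, the SAP models the worst day of each week and then single readings from week 6, and it calls an unranked residual category ordinal

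*SAP*

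**What the plan says.** Protocol 2.5 defines four categories from the pain score and analgesic use: complete response, partial response, progression, and a remainder. On the summary it says: "We intend to report the best response during follow-up". On the remainder it says: "An indeterminate response is any response not captured in the above definitions".

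SAP, Analysis, item G takes another route. "For each of the first five weeks, where daily measurements are recorded, the worst response will be used for analysis", and then: "Changes in ICPRE score over time (repeated measurement) will be analyzed using Generalized Linear Mixed Models". Item H repeats the worst-response rule for duration of response. The best response over follow-up appears nowhere in the SAP.

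The schedule is in SAP, Trial design: "treatment site pain (Numeric Pain Rating Scale) are reported daily for 5 weeks and subsequently weekly for 4 weeks", whereas "use of medication (glucocorticoid, antiemetic, analgesic) and weight are reported weekly for 9 weeks".

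Item G lists the categories thus: "Possible responses are “Complete response”, “Partial response”, “Pain Progression” and “Intermediate response". The fourth has changed its name from the protocol's indeterminate, and the SAP gives neither a definition nor an order. The Analysis summary table nevertheless gives the data type for pain response as "Ordinal, repeated measurement".

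**The concern.** Three things need attention.

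1. **Two summaries, not reconciled.** The protocol announces one value per patient, the most favourable over follow-up. The SAP analyses repeated weekly values, each the least favourable of its week up to week 5. Both rules are on record and nothing says which is reported, so the choice could be made after the data are seen.

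2. **A change of measurement at week 6.** One model runs over weeks 1 to 9, but a weekly value is the worst of up to seven days before week 6 and one reading after it. If pain varies at all from day to day, the first is lower than the second on average. Item H inherits the problem: one bad day cancels a week of response in weeks 1 to 5, while from week 6 only one day is looked at.

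3. **An ordinal label on a scale without an order.** Picking the worst category of a week, or fitting an ordinal model, requires a rank for every category. The residual class has none.

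The esophagus-sparing arm accepts a compromise in target dose (protocol 6.4), and SAP item O relates target coverage to pain response. The definition of pain response should therefore be settled before analysis.

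**Working it through.** **No plan figure to reproduce.** Neither document gives an expected pain response rate, a power calculation for pain, or a day-to-day SD. The sizes below rest on assumptions; the direction does not.

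**Step at week 6.** Assumed model for the NPRS change from baseline, patient i on day j:

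X = -2.5 + b_i + e_ij, with b_i ~ N(0, 2²) and e_ij ~ N(0, s²), errors independent between days, X rounded to a whole number.

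Response is a fall of 2 or more (the pain part of protocol 2.5's partial response), with analgesics held stable. After rounding this means X < -1.5.

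- Single reading: P = Φ((-1.5 + 2.5)/√(4 + s²)). For s = 1, Φ(1/√5) = Φ(0.447) = 67%. For s = 1.5, Φ(1/2.5) = Φ(0.4) = 66%.
- Worst of k days: every one of the k days must be a response, so P = E_b[Φ((1 - b)/s)^k].

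Simulation of this model gives:

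| Day-to-day SD | Single reading | Worst of 7 | Step | Worst of 3 | Step |
|---|---|---|---|---|---|
| 0.5 | 68.5% | 56.4% | 12 | 61.3% | 7 |
| 1 | 67.2% | 43.4% | 24 | 53% | 14 |
| 1.5 | 65.4% | 32.1% | 33 | 45% | 20 |

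Each step is taken within its own row, for example 67.2 - 43.4 = 23.8 and 65.4 - 32.1 = 33.3. True pain is the same before and after week 6 in every row, so the whole step comes from the rule.

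The two step columns also show that the measured response depends on diary completion. At SD 1 the same patients show 43% with seven diary days and 53% with three. The SAP reports low compliance at the interim analysis. Its minimum of three completed days per week is written for PRO-CTC-AE, not for the pain scale.

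**Sensitivity to the model.** Two other sets of assumptions give the ratio of the week-6 to the week-5 response rate with no true change:

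- Latent-normal responder model (daily response 0.4 to 0.7, within-week correlation 0.70 to 0.99, 3 or 7 days): 1.04 to 2.9.
- NPRS model with baseline uniform on 1 to 10, response a fall of 2 or more or a score of 0: 1.2 to 7.1.

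The ratio is above 1 throughout, but its size varies widely.

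**Rank of the residual class.** Under the protocol's definitions it contains, among others:

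- stable pain with stable analgesics;
- pain down by 2 or more with an analgesic increase (not a response because of the increase, not progression because pain is not stable).

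These states have no common place on a scale. Take a week with one progression day and one residual day. In the order in which the SAP lists the categories, the residual day is the worst. If intermediate means in the middle, the progression day is. The SAP does not decide, so two analysts could build different datasets from the same diaries.

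**Analgesics.** They are recorded weekly and pain daily in weeks 1 to 5. A daily response category therefore needs a rule for carrying the weekly analgesic record to single days. None is given.

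**The case against.** The best case for the plan has four parts.

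*The two rules can coexist.* One is a patient-level summary; the other reduces each week to a value for a longitudinal model, in parallel with the weekly peak in item B. The SAP omits the protocol's summary but does not say that it is dropped. This is fair, and it is why the point is one of reconciliation. It does not remove the step at week 6.

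*Both arms share the rule and the schedule.* This stands. With week as a categorical factor, a common step goes into the week effect, and each week still compares like with like. A reader might infer that the treatment comparison is biased or cannot be interpreted; the documents do not support that. Unequal diary completion between arms could turn the worst-day rule into an apparent treatment difference, but nothing shows that completion differs, and patients are blinded to allocation. The SAP does not say how time enters the model, so the harm to the model is conditional.

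*Pain is one secondary endpoint among many.* This also stands. The documents give the check on preserved efficacy to ambulatory function as co-primary endpoint and to re-irradiation, which the trial management committee reviews. Pain response should not be read as the main safeguard.

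*The renamed category may be a slip.* Probably so, since the SAP cites the consensus definitions, and a place at the end of a list is not a rank. But the ordinal label still needs an order that no passage supplies.

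**Conclusion.** The point holds as a matter of reconciliation and definition, and should be settled before analysis. The protocol and SAP use different summaries of pain response, and the SAP does not acknowledge the difference. As written, items G and H build an artificial improvement into week 6: about 12 to 33 points with seven completed days (SD 0.5 to 1.5), and 14 to 20 with three (SD 1 to 1.5). This assumes a mean change of -2.5, between-patient SD 2, independent daily errors and stable analgesics. Reported level, time course and duration are affected; a between-arm bias is not shown. Neither the worst response nor an ordinal model is well defined while the residual class has no rank.

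A reader might also infer that the choice between best and worst changes the response rate about twofold. The documents contain nothing from which that follows. Best response over follow-up divided by the week-5 worst-day rate is 1.2 to 6.7 in the latent model and 1.4 to 18.5 in the uniform-baseline NPRS model. It is only 1.03 to 1.35 if both sides are best-over-follow-up summaries per patient (best of all days against best of the weekly values). No single factor should be quoted.

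**What to change.** In the SAP:

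1. Restore the protocol's name and definition of the indeterminate category.
2. Model responder (complete or partial) versus non-responder with a binomial mixed model, with week as a categorical factor and a treatment-by-week term. Indeterminate counts as non-response, so it needs no rank against progression.
3. In G and H, replace the worst day by a weekly value that is not pushed in one direction by the number of diary days, for example the week's median NPRS with that week's analgesic record. This also removes the need for daily analgesic data. State the minimum number of days for the pain scale. The alternative is to analyse weeks 1 to 5 and weeks 6 to 9 separately. A fixed weekday is less attractive: it discards up to six of seven readings in a trial with low compliance.
4. State that the protocol's best response is reported as a descriptive summary, with the number of readings per arm beside it. It should not be the headline, because it too depends on how many readings exist: in the model above with SD 1 to 1.5, it rises from 65-67% on one day to 94-98% over 39 readings (5 × 7 + 4).

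The cost is SAP wording and a little more analysis work. The model no longer separates complete from partial response, or progression from other non-response; these can still be tabulated by week and arm.

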1.1 Metastatic spinal cord compression

Metastatic spinal cord compression (MSCC) is a feared complication of metastases to the vertebra. Approximately 5-10 percent of patients with metastatic cancer experience MSCC, most commonly patients with lung-, breast-, prostate and renal cancer.¹ MSCC is a disabling condition that can lead to pain, disablement of sensory and motor function distal to the injury.² Early detection and onset of treatment is key to improve outcome results. Diagnosis is typically set through either CT or MRI scan; however, MRI is the preferred modality for diagnosing.³ Symptoms are severe, unremitting pain, progressive discomfort, sensory symptoms, function deficits and bladder or bowel dysfunction⁴. Treatment is mainly high dose steroids to decrease edema and radiotherapy. Surgery is offered, when possible, to patients in good performance status and followed by radiotherapy². Interventions mainly aim at pain relief and preserving motor functions. A small fraction of patients with highly chemo-sensitive tumors are offered chemotherapy.⁴ The performance status at the time of diagnosis is the main determining factor of the post-treatment outcomes, with patients with lower-extremity function and sensation at the onset of treatment having a longer survival time⁴. When MSCC is diagnosed, life expectancy is typically short, with a 2-year survival of approximately 10% and a median survival of less than 6 months.^{2,5} As treatment is palliative Quality of Life (QoL) is important, however, patients may experience early toxicity after radiotherapy, paradoxically causing reduced QoL.^{5,6}

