2.4 Definition of endpoint related concepts

- The duration of patient reported gastric-oesophageal toxicity is measured as the time from an increase in gastro-oesophageal symptom score to a return to baseline
- Reirradiation rate is defined as fraction of patients getting reirradiation, where the same spine levels are included in the irradiated volume
- OS is defined as time from inclusion until death from any cause
- diabetes developed during glucocorticoid treatment will be defined as two random plasma glucose measurements $\geq 11,1$ mmol/L.
- Time-in-range is defined as the percent of time glucose value is in normal range (3,9-10 mmol/L)
- Time above range is defined as the percent of time the glucose value is above normal range
- Time below range is defined as the percent of time the glucose value is below normal range
- Coefficient of variation for glucose is calculated as **(Standard Deviation / Mean) * 100**

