6.4 Esophagus sparing radiotherapy vs. standard treatment

For the patients in the standard arm, a standard radiotherapy plan computed using VMAT technique aiming at covering the PTV with at least 90 % of the prescribed dose and not taking the dose to the esophagus and/or stomach into account.

For the patients in the interventional arm, a plan using VMAT technique is computed aiming at keeping the maximum dose to the esophagus and/or stomach as described in Table 4. Even if it means compromising the dose to the PTV and CTV.

Patients randomized to esophagus sparing radiotherapy needing reirradiation (**other target that primarily prescribed**) during the 9 weeks of FU, will receive esophagus sparing radiotherapy for the second target.

	Maximum Physical Esophageal Dose ($D_{0,027\text{cm}^3}$) (Gy)		Max. Esophageal Dose in EQD2 ($D_{0,027\text{cm}^3}$) (Gy), $\alpha/\beta = 3$ Gy	
Fractionation (Dosis (Gy) x Fraction)	Standard arm	Esophagus sparing arm	Standard arm	Esophagus sparing arm
5 Gy x 5	25	8,5	40	8
3 Gy x 10	30	10	36	8
10 Gy x 1	10	5	26	8
8 Gy x 1	8	5	17,6	8

Table 4. Maximum esophageal dose. Standard arm vs. esophagus sparing arm.

7 HbA_{1c} and Flash glucose monitoring

HbA_{1c} will be measured at baseline, which is standard procedure in one of the participating centers.

²³ In order to obtain ambulatory glucose profiles for retrospective glucose data analysis we will use a blinded professional sensor-based Flash glucose monitoring system (FreeStyle Libre Pro™; Abbott Diabetes Care, Witney, UK).^{19,20} The sensor is worn on the upper arm for 14 days. The sensor is factory calibrated which means that, after activating the sensor at baseline, no further intervention during the 14-day wear is required. As the sensor is blinded, data are not visible to participants or investigators during sensor wear. The sensor automatically captures and stores glucose data every 15 min (96 glucose readings/day). After 14 days the sensor is dismantled, and glucose data are wirelessly transferred to the pro-reader. Summary glucose reports are generated using the system software. Patients in our study will be followed for 28 days after start of radiotherapy treatment requiring one sensor change. This will include time without glucocorticoid treatment.

The patients participating in this part of the study will not be subject to standard glucose measurements; instead they will be thoroughly instructed to contact the PI if symptoms of hyperglycaemia should occur.

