Table 2: Distribution of ambulatory function. The conventional arm follows the SCORAD trial (Hoskin et al., 2019).

Recruitment, withdrawal, and follow-up

Enrollment, intervention, allocation, follow-up, and data analysis will be summarized in a CONSORT diagram in accordance with CONSORT 2010 guidelines (4)

Statistical principles

Confidence intervals and P values

Level of significance: $p < 0.05$ with no adjustment for multiplicity. Confidence intervals are reported at 95 % limits (bound by zero) and calculated by the binominal distribution for rates and as per Kaplan-Meier method for time-to-event analyses.

Analysis

We will report our data in accordance with the CONSORT 2010 guidelines including the CONSORT Patient-Reported Outcome (PRO) extension (4,5) .

Analyses will be performed per-protocol for all patients who have received any study treatment.

Primary analysis of NCI-PRO-CTC-AE toxicity will only include weeks where ≥ 3 days questionnaires are completed.

Primary analysis of EQ-5D-5L and EORTC-QLQ-C30 will only include completed questionnaires.

All CTC-AE and PRO-CTC-AE grades will be reported.

Missing data will be described in detail, see missing data section.

A. Co-primary endpoints

1. Peak dysphagia (difficulty swallowing) measured by NCI-PRO-CTC-AE within 5 weeks after start of radiotherapy (daily measurements).

PRO-CTC-AE responses are scored from 0 to 4, with 0 representing "None" and 4 representing "Very severe". For each patient the peak value within 5 weeks after start of radiotherapy (daily measurements) will be included in the analysis. Difference in scores between treatment arms will be compared using Wilcoxon rank-sum test.

2. Ambulatory function measured by EQ-5D-5L mobility dimension at 9 weeks after start of radiotherapy.

EQ-5D-5L measures individual generic health status using 5 dimensions: mobility, self-care, usual activities, pain/discomfort, and anxiety/depression. Each dimension has 5 levels depending on the severity of symptoms, with 1 representing “No problems” and 5 representing “Extreme problems”. Difference in scores between mobility dimension treatment arms will be compared using Wilcoxon rank-sum test.

B. Severity of dysphagia, nausea and dyspepsia measured by NCI-PRO-CTC-AE [Time Frame: Week 1-9 after start of radiotherapy (repeated measurement)].

CTC-AE responses are scored from 0 to 4, with 0 representing “None” and 4 representing “Very severe”.

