Duration of pain response measured by the ICPRE score will be presented graphically in separate figures. For each of the first five weeks, where daily measurements are recorded, the worst response will be used for analysis.

Mean response duration in each group will be compared using Wilcoxon rank-sum test.

I. Quality of life [Timeframe: weekly, 1-9 weeks after start of RT]: measured by EORTC-QLQ-C30 and EQ-5D-5L will be scored per instruction of the instrument and summarized for each arm. The scores will be presented graphically in separate figures. Changes in scores over time (repeated measurement) will be analyzed using Generalized Linear Mixed Models.

J. EORTC QLQ-C30, other domains [Timeframe: weekly, 1-9 weeks after start of RT]: Descriptive statistics of QLQ-C30 domains will be performed. Changes over time (repeated measurement) will be analyzed using Generalized Linear Mixed Models.

K. Weight [Timeframe: weekly week 1-9]: Changes in weight from baseline (repeated measurement) will be analyzed using Generalized Linear Mixed Models

- L. **Hospitalization:** Hospitalization rate will be calculated as days hospitalized of days alive during the 9-weeks follow-up and compared between treatment arms.
- M. **Re-irradiation rate (primary treatment site):** The results will be reported for each treatment group using time-to-event analysis (Kaplan-Meier), and differences in curves will be tested using the Log-rank test.
- N. **Overall survival** [Time Frame: Analysis will be made up to 2 years after study completion] is defined as time from inclusion until death from any cause. Overall survival will be reported off the Kaplan-Meier curves. Differences in survival curves will be tested by Log-rank test. If reached, the median survival time will be reported with a 95% confidence interval.
- O. **Analysis of correlation** between target coverage and pain response, re-irradiation (primary treatment site) and ability to walk.

Reporting of the radiation details

The following radiation details will be reported and compared between the two arms using Wilcoxon rank-sum test.

1. Delivery: VMAT, IMRT or opposing fields

2. Target doses and volumes:

- PTV V80, V90: the volume of the PTV (%) that is covered by the 80% and 90% isodose.
- CTV V80, V90: the volume of the CTV (%) that is covered by the 80% and 90% isodose
- Esophagus D0.027cm³, D1cm³, D2cm³ and D5cm³ (Gy)
- Posterior pharyngeal wall D0.027cm³, D1cm³, D2cm³ and D5cm³ (Gy)

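### Re-irradiation has two conflicting analyses in the SAP and no rule for deaths; if deaths are censored, one minus Kaplan-Meier overstates the fraction of patients re-irradiated

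*SAP*

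**What the plan says.** Four places bear on this endpoint.

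- **SAP, Analysis, item M:** "The results will be reported for each treatment group using time-to-event analysis (Kaplan-Meier), and differences in curves will be tested using the Log-rank test". No time points are given.
- **SAP, Analysis summary, re-irradiation row:** the measure is "Number of patients receiving re-irradiation in each arm (absolute numbers and" percentages), at "3, 6- and 12-months after inclusion". The data type, which opens "Continuous, mean [range", is that of a measured quantity, and the test is Wilcoxon rank-sum.
- **SAP, Confidence intervals and P values:** intervals are "calculated by the binominal distribution for rates and as per Kaplan-Meier method for time-to-event analyses". Re-irradiation is planned as both.
- **Protocol 2.4:** "Reirradiation rate is defined as fraction of patients getting reirradiation, where the same spine levels are included in the irradiated volume".

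The SAP's Missing data section reports how many participants died but gives no rule for deaths in this endpoint. Protocol 1.1 expects "a 2-year survival of approximately 10% and a median survival of less than 6 months".

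**The concern.** Item M and the table differ in the quantity estimated, the data type and the test, and the SAP does not say which gives the result. With significance at 0.05 and no multiplicity adjustment, the team could choose between two rates and two tests after seeing the data.

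The missing rule for deaths makes the difference large. By the protocol's own expectation at least half of the patients will have died by 6 months. Censoring at death is the usual default when a Kaplan-Meier curve is drawn for re-irradiation alone. One minus that curve then answers what would happen if nobody died, which is not the fraction in Protocol 2.4.

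The endpoint matters because the experimental plan holds to its esophageal limit "Even if it means compromising the dose to the PTV and CTV". Re-irradiation is therefore one signal of under-treatment, beside ambulatory function and pain response. Protocol 8.3 also has the trial management committee look at the one-year rate, and refers to the sample size calculation for what counts as excessive. That calculation contains no re-irradiation rate. Of the planned time points, twelve months is where the two estimators differ most.

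**Working it through.** The documents state no re-irradiation rate, event count or power, so there is no figure to reproduce. The check has three steps.

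**1. What each analysis estimates.** Let *r* be the monthly re-irradiation hazard and *d* the monthly death hazard, both constant.

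- One minus Kaplan-Meier, deaths censored: 1 − exp(−*rt*).
- Fraction of patients re-irradiated (cumulative incidence): *r*/(*r*+*d*) × [1 − exp(−(*r*+*d*)*t*)].

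The first exceeds the second whenever *d* > 0. The direction does not depend on the assumed values.

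**2. Size.** From the protocol: median survival below 6 months, about 10% alive at 2 years. Assumed: *r* = 0.02 per month. With a 6-month median, *d* = ln 2/6 = 0.1155. At 12 months:

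- One minus Kaplan-Meier: 1 − exp(−0.24) = 21.3%.
- Fraction: 0.02/0.1355 × [1 − exp(−1.626)] = 0.1476 × 0.803 = 11.9%.
- Ratio: 1.80.

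| Survival assumption | Time | One minus KM | Fraction | Ratio |
|---|---|---|---|---|
| Median 6 months | 3 months | 5.8% | 4.9% | 1.18 |
| Median 6 months | 6 months | 11.3% | 8.2% | 1.38 |
| Median 6 months | 12 months | 21.3% | 11.9% | 1.80 |
| Median 4 months | 12 months | 21.3% | 9.3% | 2.29 |
| 10% at 2 years (*d* = −ln 0.10/24 = 0.0959, median 7.2 months) | 12 months | 21.3% | 13.0% | 1.65 |
| Median 9 months | 12 months | 21.3% | 14.2% | 1.50 |

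The last two rows have medians above the protocol's expectation and show a smaller effect.

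Timing also matters. With a 6-month median, the 12-month ratio is:

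- 1.18 if all events fall in months 0–3;
- 1.31 if the hazard decays as 0.06 × exp(−*t*/3) (16.2% against 12.3%);
- 2.24 if all events fall in months 3–12 (16.5% against 7.4%).

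The result is not tied to one rate. With a 6-month median and an assumed true 12-month fraction of 5%, 10%, 15% or 20%, one minus Kaplan-Meier gives 9.1%, 18.1%, 26.8% or 35.2%. A Weibull death curve through 50% at 6 months and 10% at 24 months gives nearly the same ratios (1.83 to 1.77). A simulation of 200,000 patients with a true 10% returned 9.97% and 17.96%.

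**3. The two tests.** On a yes/no outcome the Wilcoxon test compares proportions. For 12/100 against 6/100 it gives p = 0.139, identical to the (N−1) chi-square. Log-rank with deaths censored compares hazards. Simulated trials with 100 per arm, 12-month follow-up and assumed hazards (4,000 trials per scenario) gave:

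| Hazards | Median survival (months) | Log-rank p<0.05 | Wilcoxon p<0.05 | Tests disagree |
|---|---|---|---|---|
| 0.02 v 0.04 | 6 and 6 | 50% | 46% | 10% |
| 0.02 v 0.04 | 6 and 4 | 48% | 20% | 28% |
| 0.02 v 0.02 | 6 and 4 | 5% | about 9–10% | about 8% |

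Repeat runs of the first two rows agree within about 3 points (51/47/10% and 45/20/26%). In the last row the hazards are equal. The Wilcoxon test rejects more often than 5% because the true fractions differ through mortality alone.

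**The case against.** The strongest reply has four parts.

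- **A curve and a percentage can be reported together, and the table may hold a slip.** The hospitalization row above has the same data type and test, so those entries may have been carried over. This is plausible but cannot be shown from the documents. Two tests still stand with no order between them.
- **The table does imply a rule for deaths.** A percentage of patients in each arm naturally keeps patients who died in the denominator, and then it matches Protocol 2.4 when follow-up is complete. This largely stands. What the table lacks is a stated denominator, so the gap on deaths mainly concerns item M. Likewise, the interval paragraph is clear in itself and only inherits the conflict.
- **The overstatement is conditional.** It arises only if deaths are censored and one minus Kaplan-Meier is read as the rate. That is correct. Log-rank with deaths censored remains a valid comparison of cause-specific hazards.
- **The numbers are assumed.** They are. Nothing in the documents predicts the survival difference between arms behind the 28% disagreement, and with equal mortality the tests mostly agree. The direction of the overstatement needs none of these assumptions.

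**Conclusion.** The concern holds. The contradiction between item M and the summary table is visible in the text and needs no modelling. If deaths are censored, one minus Kaplan-Meier is too high as an estimate of the protocol's fraction. In the scenarios with a 6-month median the 12-month ratio is about 1.2 to 2.2 depending on when events occur, and 1.8 with a constant hazard. Under that constant hazard it is about 1.2 at 3 months and 1.4 at 6 months. These sizes rest on assumed re-irradiation hazards.

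With similar mortality the choice of test changes the conclusion in roughly one trial in ten in the scenario studied. If mortality differs by arm, the tests answer different questions. This is a secondary endpoint, so the change should be made but does not threaten the co-primary analyses.

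**What to change.** Use the same text in item M and in the summary table:

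> Time from inclusion to first re-irradiation of the primary treatment site. Death without re-irradiation is a competing event. Patients alive without re-irradiation are censored at the last date covered by their treatment records. Cumulative incidence (Aalen-Johansen) is reported by arm at 3, 6 and 12 months with 95% confidence intervals. Arms are compared with the log-rank test on the cause-specific hazard, deaths censored. Cumulative incidence of death without re-irradiation is shown by arm alongside.

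Then:

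- delete the Wilcoxon entry and the continuous data type from the re-irradiation row;
- state in the confidence-interval paragraph that this endpoint uses Aalen-Johansen intervals;
- state whether second entries of patients included twice count here, because the SAP excludes them from time-to-event analyses but names only survival.

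Gray's test can be added as an option.

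The cost is SAP wording. Re-irradiation and survival already come from treatment records, and R is already listed. Reported rates will be lower than Kaplan-Meier rates. Cumulative incidence can also hide a higher hazard in an arm with more deaths: a hazard of 0.026 with a 4-month median and 0.02 with a 6-month median both give 11.9% at 12 months. That is why the log-rank test is kept and deaths are shown by arm.
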